6.5 Dependent Variables (Outcomes)

Anastomotic leak within 30 days post-index procedure. AL will include all new AL cases identified during the index admission and those identified during a new admission within 30 days post-index procedure. A 30-day follow-up period is chosen as AL occurs at a median of 12 days (range, 3-30 days) after a colorectal procedure¹⁴ and it is the standard post-operation follow-up study period for most studies assessing AL after stapled anastomosis.

As there is no specific diagnosis code for AL in the International Classification of Diseases, 10th Revision, Clinical Modification (ICD-10-CM) taxonomy, the cumulative incidence of AL can only be estimated via either surrogate diagnoses or procedures which usually occur concomitantly with a leak, e. g., an abscess, peritonitis, a fistula or a post-index surgery stoma formation — a surgical treatment for severe AL.

As such, the presence of an ICD-10-CM diagnosis code for anastomotic leak surrogate diagnoses, such as fistula of intestine, peritonitis, or peritoneal abscess during the index admission or re-admission within 30 days post-index procedure, or the presence of an ICD-10-Procedure Coding System (ICD-10-PCS) procedure code indicating a diverting stoma occurred within 1-30 days post-index procedure will be used to define AL in the PHD. A similar approach was used in other studies assessing the risk of AL using electronic health records (EHR), such as PHD¹⁷ or Nationwide Inpatient Sample database¹⁸. The list of diagnosis codes is summarized in [Table A- 2](#), and the list of ICD-10-PCS codes indicating diverting stoma is summarized in [Table A- 3](#).

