6.8 Sample Size and Study Power

A feasibility analysis identified more than 10,000 patients in PHD between 2019 and 2021 who were treated surgically with the use of Ethicon Manual Circular Stapler. Among those, approximately 6,000 patients had a left-sided colorectal surgery.

Among approximately 13,000 patients who were treated surgically with Medtronic EEA™ Circular Stapler with DST Series™ Technology, about 6,000 patients had a left-sided colorectal surgery in the PHD.

A similar analysis identified 623 patients in PHD between 2019 and 2021 who underwent surgical procedures where Medtronic EEA™ Circular Stapler with Tri-Staple™ Technology was used. Among those, 526 underwent a left-sided colorectal surgery.

The final sample sizes for the study will vary based on applying the inclusion and exclusion criteria, as well as additional data beyond 2021 being available from PHD.

Power estimates assuming different combinations of relative risk, sample size, and the cumulative incidence of AL in the comparison cohort—Medtronic EEA™ Circular Stapler with Tri-Staple™ Technology— are provided in [Table 2](#)

[Table 2.](#) The calculations assumed one-sided tests at a significance level of 0.025 (or type I error of 0.025). The estimated cumulative incidence of AL among patients who underwent a colorectal surgery with the use of Medtronic EEA™ Circular Stapler with Tri-Staple™ Technology ranges from 2% to 3.5% in the literature.^{8,12}

[Table 2: Power estimation, by relative risk](#)

Relative Risk	AL risk in the comparison cohort	Sample size in the target cohort	Sample size in the comparison cohort	Power
2.5	3%	6,000	500	0.995
2	3%	6,000	500	0.856
1.5	3%	6,000	500	0.324
2.5	2%	6,000	500	0.938
2	2%	6,000	500	0.642
1.5	2%	6,000	500	0.209

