8 LIMITATIONS OF RESEARCH METHODS

The study is observational in nature and thus susceptible to limitations.

The first relates to the validity of the diagnosis of anastomotic leak. As with any other non-interventional database study using health insurance administrative claims or electronic health records (EHR), identification of medical events, such as anastomotic leak or co-morbidities, is limited to data that are captured as part of the medical record or claims, which are not primarily collected for research purposes, and will rely on appropriate diagnostic codes to detect these events. As there is no specific diagnosis code for anastomotic leak in the ICD-10-CM taxonomy, the anastomotic leak surrogate diagnoses, such as abscess of intestine, fistula of intestine, peritonitis, or peritoneal abscess, will be used to define AL in the PHD. Misclassification bias can result if study patients are not categorized correctly with regards to outcome, however, should be non-differential between the comparison groups.

Misclassifications due to the secondary use of billing data may also lead to under or overestimation of cohort size. For example, the search strategy designed in this study may underestimate the prevalence of products in the database if the search strategy missed any incorrectly coded entries for study devices such as misspellings leading to misclassification of the exposure. However, there is no evidence that the misclassification bias would be differential between the comparison groups.

Indication for product usage is not specifically stated in the PHD; it is being inferred based on the primary procedure codes recorded during the index hospitalization. Therefore, misclassification of indication in this study is possible but should be non-differential between the comparison groups.

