APPENDIX A: DIAGOSIS AND PROCEDURE CODES

Table A- 1: Procedure Codes (ICD-10-PCS) for Left-sided Colorectal Surgery

CODE	CODE DESCRIPTION
ODTG%	Resection, large intestine, left
ODTM%	Resection, Descending Colon
ODTN%	Resection, Sigmoid Colon
ODTP%	Resection, Rectum
ODBG%	Excision, large intestine, left
ODBM%	Excision, Descending Colon
ODBN%	Excision, Sigmoid Colon
ODBP%	Excision, Rectum
ODQM%	Repair, Descending Colon
ODQN%	Repair, Sigmoid Colon
ODQP%	Repair, Rectum

'%' at the end of the code denotes any value for subsequent characters.

'%' in the middle of the code denotes any valid value for a character in that specific position

RWE23-SAF-001:Comparative safety study to assess the risk of AL of 2-row vs 3-row circular staplers

Table A- 2: Diagnosis Codes (ICD-10-CM) Indicating Anastomotic Leak

CODE	CODE DESCRIPTION
K63.2	Fistula of intestine
K65.0	Generalized Peritonitis
K65.1	Peritoneal abscess
K91.89	Other postprocedural complications and disorders of digestive system
Y83.2	Surgical operation with anastomosis, bypass or graft as the cause of abnormal reaction of the patient, or of later complication, without mention of misadventure at the time of the procedure

Table A- 3: Procedure Codes (ICD-10-PCS) for Diverting Stoma

CODE	CODE DESCRIPTION
0D18%%4	Bypass Small Intestine to Cutaneous
0D1B%%4	Bypass Ileum to Cutaneous
0D1E%%4	Bypass large intestine to Cutaneous
0D1H%%4	Bypass Cecum to Cutaneous
0D1K%%4	Bypass Ascending Colon to Cutaneous,
0D1L%%4	Bypass Transverse Colon to Cutaneous
0D1M%%4	Bypass Descending Colon to Cutaneous
0D1N%%4	Bypass Sigmoid Colon to Cutaneous

'%' in the middle of the code denotes any valid value for a character in that specific position

RWE23-SAF-001:Comparative safety study to assess the risk of AL of 2-row vs 3-row circular staplers

Table A- 4: Diagnosis Codes (ICD-10-CM) for Comorbid Conditions

Comorbid conditions	CODE	DESCRIPTION
Alcohol dependency	F10.2%	Alcohol dependence
Cardiovascular diseases	G45%, G46%, I60%, I61%, I62%, I63%, , I65%, I66%, I67%, I68%, I69%, H34.0%	cerebrovascular disease
	I43, I50%, I09.9, I11.0, I13.0, I13.2, I42.0, I42.5, I42.6, I42.7, I42.8, I42.9	congestive heart failure
	I20%, I23%, I24%, I25%	ischemic heart disease
	I21%, I22%	myocardial infarction
	I70%, I71%, I73.1, I73.8%, I73.9, I77.1, Z95.8%, Z95.9	peripheral artery disease
Chronic obstructive pulmonary disease	J44.0, J44.1, J44.9	Chronic obstructive pulmonary disease

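### Two non-specific codes in Table A-2 (K91.89 and Y83.2) each count as anastomotic leak on their own, and no sensitivity analysis tests a narrower outcome definition

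*Supplement*

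**What the plan says.** Section 6.5 notes that ICD-10-CM has no code specific to AL and therefore uses surrogates that ordinarily accompany a leak. A case is "the presence of an ICD-10-CM diagnosis code for anastomotic leak surrogate diagnoses, such as fistula of intestine, peritonitis, or peritoneal abscess", recorded in the index stay or in a readmission within 30 days, or a diverting-stoma procedure code on days 1 to 30. For the diagnosis codes the section refers to Table A-2.

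Table A-2 (Appendix A) lists five codes on an equal footing: K63.2 (fistula of intestine), K65.0 (generalized peritonitis), K65.1 (peritoneal abscess), K91.89 ("Other postprocedural complications and disorders of digestive system") and Y83.2 ("Surgical operation with anastomosis, bypass or graft as the cause of abnormal reaction of the patient, or of later complication"). Neither a footnote nor the text requires any of them to appear together with another.

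Sections 6.2, 6.5, 6.9.1.2 and 8 name abscess, peritonitis and fistula and, except in Section 8, stoma. None mentions the content of K91.89 or Y83.2. Section 8 lists "the anastomotic leak surrogate diagnoses, such as abscess of intestine, fistula of intestine, peritonitis, or peritoneal abscess", but Table A-2 has no row for abscess of intestine. Section 8 also acknowledges outcome misclassification and expects it to be non-differential. The only sensitivity analysis (Section 6.9.4) restricts the sample by hospital enrollment and leaves the outcome unchanged.

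**The concern.** AL is the study's only outcome, so Table A-2 drives every primary and secondary estimate. K91.89 is a residual class of digestive complications after a procedure. Y83.2 attributes some later complication to an operation with anastomosis, bypass or graft without saying what the complication was. Every patient in the cohort had left-sided colorectal surgery with a circular stapler billed, so either code could be recorded for a complication other than a leak, and that patient would become a case.

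Under the plan's own non-differential assumption, such false positives move a true RR above 1 toward 1. The study asks whether 2-row staplers carry more AL than the 3-row device, so this is the direction in which a safety signal is lost. Section 8 does not say so. The same false positives inflate the cumulative incidence reported for primary objective 1. Because no analysis varies the definition, the report would not show how many cases rest on these two codes.

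**Working it through.** **Inputs from the plan.** Section 6.8: "The calculations assumed one-sided tests at a significance level of 0.025 (or type I error of 0.025"); comparator AL risk that "ranges from 2% to 3.5% in the literature"; Table 2 rows "2 3% 6,000 500 0.856" and "2 2% 6,000 500 0.642" (RR, comparator risk, target n, comparator n, power).

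**Input not in the plan.** The probability f that a patient without a leak is counted as a case through K91.89 or Y83.2 alone. I assume 1% to 10%, equal in both arms, with every true leak captured.

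**Step 1: reproduce Table 2.** Pooled-variance normal approximation, no continuity correction:

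power = Φ{(|p1 − p0| − 1.96·s0) / s1}, with s0 = √[p̄(1−p̄)(1/6000 + 1/500)] and s1 = √[p1(1−p1)/6000 + p0(1−p0)/500].

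For p1 = 0.06 and p0 = 0.03: p̄ = (6000×0.06 + 500×0.03)/6500 = 0.0577, s0 = 0.01085, s1 = 0.00822. Then (0.03 − 1.96×0.01085)/0.00822 = 1.06, and Φ(1.06) = 0.856, as stated. All six rows of Table 2 reproduce within 0.001.

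**Step 2: add false positives.** Observed risk in each arm: q = p + (1 − p)f. Observed RR = q1/q0. Power uses the Step 1 formula with q in place of p.

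Worked case, f = 5%: q0 = 0.03 + 0.97×0.05 = 0.0785; q1 = 0.06 + 0.94×0.05 = 0.107; RR = 0.107/0.0785 = 1.36.

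| f (assumed) | Observed risks, true 6% vs 3% | RR | Power | RR, true 4% vs 2% | Power |
|---|---|---|---|---|---|
| 0 | 6.0% vs 3.0% | 2.00 | 0.856 | 2.00 | 0.642 |
| 1% | 6.9% vs 4.0% | 1.75 | 0.77 | 1.66 | 0.51 |
| 2% | 7.9% vs 4.9% | 1.60 | 0.69 | 1.50 | 0.43 |
| 5% | 10.7% vs 7.9% | 1.36 | 0.52 | 1.28 | 0.29 |
| 10% | 15.4% vs 12.7% | 1.21 | 0.36 | 1.15 | 0.19 |

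The share of comparator cases that are false is (1 − p0)f/q0. With p0 = 3% it is 0.0194/0.0494 = 39% at f = 2% and 0.0485/0.0785 = 62% at f = 5%.

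**Step 3: the opposite error.** If a narrower definition misses leaks equally in both arms but admits no false ones, each risk is multiplied by the sensitivity, so the RR stays at 2 and only power falls. From 6% vs 3%: sensitivity 0.8 gives power 0.745, 0.7 gives 0.670, 0.6 gives 0.582.

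**Step 4: unequal false positives.** With true RR 1 at 3% and f of 5% in the comparator and 7% in the target arm, the observed RR is (0.03 + 0.97×0.07)/(0.03 + 0.97×0.05) = 0.0979/0.0785 = 1.25. With the two rates exchanged it is 0.80. Dilution toward 1 is therefore a consequence of the non-differential assumption and not a certainty.

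**The case against.** The text's list is introduced as examples, includes a stoma on days 1 to 30, and refers the reader to Table A-2. A reader might infer that the text defines AL as fistula, peritonitis and abscess only and that the table contradicts it. The wording does not support that. What stands is that the examples illustrate a stated criterion, and these two codes do not meet it by their descriptions.

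Breadth has a rationale. AL has no code of its own, so some leaks may well be recorded only in a residual class such as K91.89. Section 6.5 also cites earlier database studies with a similar approach, although the plan does not show their code lists or any validation of this one. Removing K91.89 would trade false positives for missed leaks. Step 3 shows the price: if K91.89 alone carried 30% to 40% of true leaks (also an assumption), power would fall to 0.670 to 0.582, a loss comparable to f between 2% and 5%. This part of the objection stands for K91.89. It is weaker for Y83.2, which describes no complication at all.

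A reader might also take the dilution figures as the bias to expect. They are not: nothing in the documents fixes f, and dilution needs equal false-positive rates and a true RR other than 1. Nor would a pairing rule repair K91.89. Pairing it with K63.2, K65.0 or K65.1 adds nothing because those codes already qualify alone, and K91.89 with Y83.2 could still be a complication other than a leak.

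Section 8 does disclose that surrogate codes may misclassify the outcome. It does not state the direction of the effect.

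**Conclusion.** The point holds in a limited form and is one that should be fixed. As written, either K91.89 or Y83.2 alone makes a patient an AL case, neither matches the plan's description of a leak surrogate, and no planned analysis would reveal how much the results depend on them. If false positives are equally frequent in both arms and the true RR exceeds 1, the RR is biased toward 1 and the incidence upward. The size cannot be determined from the documents. For a true RR of 2 at 3% comparator risk and full sensitivity, f of 1% to 10% gives an RR of 1.75 to 1.21 and unweighted power of 0.77 to 0.36, against 0.856 stated. The documents do not support saying that the primary result will be diluted by any particular amount, or that K91.89 must be removed from the primary definition.

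**What to change.** 1. Do not count Y83.2 alone as AL. Since every other Table A-2 code already qualifies by itself, this amounts to removing Y83.2 from the outcome list.
2. Prespecify a sensitivity analysis of both primary comparisons with AL defined as K63.2, K65.0, K65.1 or a stoma on days 1 to 30. Report, for each arm, how many cases under the primary definition rest only on K91.89 or Y83.2.
3. State in Section 8 that non-differential false positives bias the RR toward 1. Reconcile the mention of abscess of intestine with Table A-2, by adding a code or deleting the phrase.
4. Give a reason for keeping or dropping K91.89 in the primary definition. Either choice is defensible if the narrow analysis is reported beside it.

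The cost is a code-list edit, one repeated analysis of existing data, and some loss of sensitivity, and so of power, under the narrower definition. Table A-2 also drives the present-on-admission exclusion in Section 6.3, so an edit may change the cohort slightly and with it the propensity weights. The plan should say whether that exclusion follows the revised list. The changes should be made before the outcome data are analyzed.

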6.6.2 Procedural Characteristics

- Surgical site (indication for product usage): primary organ involved in the index procedure as defined by the primary procedure code (See [Table A- 1](#)).
 - Rectum
 - Sigmoid
 - Descending colon
 - others
- Primary diagnosis: Primary ICD-10-CM discharge diagnosis code recorded during the index hospital admission will be used to designate indication for surgery (See [Table A- 5](#)).
 - Malignant neoplasms
 - Benign neoplasm

RWE23-SAF-001:Comparative safety study to assess the risk of AL of 2-row vs 3-row circular staplers

- Diverticular disease or Diverticulitis
 - Intestinal obstruction
 - Others
- Diverting stoma (yes, no) occurred prior to or on the same day as the index procedure (i.e., left-sided colorectal surgery) during the index admission: defined as the presence of an ICD-10-PCS procedure code indicating diverting stoma (see [Table A- 3](#)) identified prior to or on the same day as the index procedure during the index admission
 - Surgical approach:
 - Open
 - Laparoscopic
 - Robotic assisted
 - Unknown

Surgical approach is determined by the primary and secondary procedure code. For a *primary* procedure code in ICD-10-PCS, the fifth character of the code explicitly identifies the surgical approach with '0' standing for an open procedure and characters other than '0' representing a laparoscopic approach, unless the presence of a *secondary* procedure code (i.e., ICD-10-PCS: 8E0W%CZ—Robotic Assisted Procedure of Trunk Region) indicating a robotic assistance procedure. Conversions from laparoscopic or unknown surgical approach to open surgical approach will be categorized as open surgery (the procedure code list for conversions is provided in [Table A- 6](#)).

- Year of index procedure
- Admission type during index procedure (elective admission; emergent or urgent admission): elective surgery was scheduled in advance, while urgent or emergency surgery was done because of an urgent medical condition. We assume an index encounter categorized as elective indicates a procedure scheduled in advance, while urgent or emergency index encounter admissions reflect an urgent medical condition.

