6.9.2 Primary Comparative analysis

The goals of comparative analyses are to: 1) estimate the RR of AL for Ethicon Manual Circular Staplers compared to Medtronic EEA™ Circular Stapler with Tri-Staple™ Technology; 2) estimate the RR of AL for the Medtronic EEA™ Circular Stapler with DST Series™ Technology compared to Medtronic EEA™ Circular Stapler with Tri-Staple™.

The primary analyses will be conducted separately for the comparison between Ethicon Manual Circular Stapler versus Medtronic EEA™ Circular Stapler with Tri-Staple™ Technology and the comparison between Medtronic EEA™ Circular Stapler with DST™ Technology and Medtronic EEA™ Circular Stapler with Tri-Staple™ Technology. See the expected outputs in [Table B- 7](#) and [Table B- 8](#).

A propensity score weighting (PSW) method will be used to control for potential confounders by balancing the distribution of baseline demographic, clinical, and procedural characteristics between the comparison groups. The following baseline variables will be considered in the propensity score model based on their clinical relevance to the safety of the device: patient demographics (age, sex, and race), clinical characteristics (CCI, comorbid conditions, diverting stoma occurred prior to or on the same day as the index procedure), procedural characteristics (procedure year, surgical site, primary diagnosis, surgical approach, and admission type), and hospital and provider

RWE23-SAF-001:Comparative safety study to assess the risk of AL of 2-row vs 3-row circular staplers

characteristics (hospital region, hospital location, hospital setting, hospital bed size, and surgeon specialty).

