Coagulation defects	D65, D66, D67, D68.0, D68.1, D68.2, D68.3%, D68.4, D68.5%, D68.6%, D68.9	Coagulation defects
Diabetes	E11.%, E10.%, E13.%, O24.%, E08.%, Z79.4, Z79.84	Diabetes mellitus, Gestational diabetes, Secondary diabetes, long term (current) use of insulin/oral antidiabetic drugs
Hypertension	I10, I11%, I12%, I13%, I15%	Hypertension
Immunodeficiency/immunosuppression	D80%, D81%, D82%, D83%, D84%	immunodeficiencies
	Z92.25	Personal history of immunosuppression therapy
	Z79.52	Long term (current) use of systemic steroids
	B20	AIDS/HIV
Kidney disease	N18%, N19, I12.0, I13.1%, N03.2, N03.3, N03.4, N03.5, N03.6, N03.7, N05.2, N05.3, N05.4, N05.5, N05.6, N05.7, N25.0, Z49.0%, Z94.0, Z99.2	Renal diseases
Malnutrition	E41, E42, E43, E44%, E46, E63%	Malnutrition, nutritional deficiencies
Obesity	E66.0%, E66.1, E66.2, E66.8, E66.9, Z68.3%, Z68.4%	Obesity, body mass index (BMI) 30-39, BMI 40 or greater

'%' at the end of the code denotes any value for subsequent characters.

RWE23-SAF-001:Comparative safety study to assess the risk of AL of 2-row vs 3-row circular staplers

Table A- 5: Diagnosis Codes (ICD-10-CM) for Indications of Surgery

PRIMARY DIAGNOSIS	CODE	CODE DESCRIPTION
Malignant neoplasms	C18.6	Malignant neoplasm of descending colon
	C18.7	Malignant neoplasm of sigmoid colon
	C18.8	Malignant neoplasm of overlapping sites of colon
	C18.9	Malignant neoplasm of colon, unspecified
	C19	Malignant neoplasm of rectosigmoid junction
	C20	Malignant neoplasm of rectum
Benign neoplasm	D12.4	Benign neoplasm of descending colon
	D12.5	Benign neoplasm of sigmoid colon
	D12.6	Benign neoplasm of colon, unspecified
	D12.7	Benign neoplasm of rectosigmoid junction
	D12.8	Benign neoplasm of rectum
Diverticular disease or Diverticulitis	K57.2%	Diverticulitis of large intestine
	K57.3%	Diverticular disease of large intestine
	K57.8%	Diverticulitis of intestine, part unspecified
	K57.9%	Diverticular disease of intestine, part unspecified
Intestinal obstruction	K56.2	Volvulus
	K56.6%	Other and unspecified intestinal obstruction

'%' at the end of the code denotes any value for subsequent characters.

Table A- 6: Diagnosis Codes (ICD-10-CM) for Conversion of Minimally Invasive Procedure to Open Procedure

CODE	CODE DESCRIPTION
Z53.31	Laparoscopic surgical procedure converted to open procedure
Z53.32	Thoracoscopic surgical procedure converted to open procedure
Z53.33	Arthroscopic surgical procedure converted to open procedure

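### Table A-5 codes 'Malignant neoplasms' from six sites only, so other cancers share the 'Others' level with inflammatory bowel disease, and the propensity score does not directly balance the mix inside that level

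*Supplement*

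**What the plan says.** Section 6.6.2 states the assignment rule: "Primary ICD-10-CM discharge diagnosis code recorded during the index hospital admission will be used to designate indication for surgery". It names four levels (malignant neoplasms, benign neoplasm, diverticular disease or diverticulitis, intestinal obstruction) plus 'Others'.

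Appendix A, "Table A- 5: Diagnosis Codes (ICD-10-CM) for Indications of Surgery", gives codes for the four named levels only. The malignant level has six: C18.6, C18.7, C18.8, C18.9, C19 and C20. They cover the descending colon, sigmoid colon, overlapping sites, colon unspecified, rectosigmoid junction and rectum. Inflammatory bowel disease has no code in Table A-5 and no row among the comorbid conditions in Table A-4.

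Section 6.9.2 puts this variable into the score, among "procedural characteristics (procedure year, surgical site, primary diagnosis, surgical approach, and admission type". It calls the score variables prespecified confounders, judges balance by the absolute standardized difference (ASD), and adds a poorly balanced score variable to the log-binomial model.

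The qualifying operations in Table A-1 include "Resection, large intestine, left".

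**The concern.** Label and code list do not match. A splenic-flexure cancer can be treated by the left large-intestine resection in Table A-1, yet its site is not among the six. The patient is then scored 'Others', as is a patient whose principal diagnosis is a gynaecological or secondary cancer. The same level takes inflammatory bowel disease and every other non-cancer indication not listed.

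Two things are at stake. First, section 6.9.2 treats indication as a confounder, but weighting, ASD and regression fallback all act on the same coarse variable. If the devices differ in what lies inside 'Others', the plan's checks can show perfect balance while that difference stays in both primary relative risks. The outcome includes fistula of intestine (K63.2) and peritoneal abscess (K65.1). On clinical grounds, which the documents do not discuss, inflammatory bowel disease can produce both without a leak, so it is a poor candidate for pooling. Second, Table B-6 serves primary objective 1 with incidences by primary diagnosis: its malignant row would omit some malignancies and its 'Others' row would combine cancer and non-cancer.

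**Working it through.** **1. The plan's own figures, for scale.** No stated figure depends on Table A-5. Table 2 fixes the setting: 6,000 target and 500 comparator patients, comparator risk 2% or 3%, and "The calculations assumed one-sided tests at a significance level of 0.025 (or type I error of 0.025". With pooled variance under the null and no continuity correction,

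power = Φ{[p₂ − p₁ − 1.96·√(p̄(1−p̄)(1/500 + 1/6000))] / √(p₁(1−p₁)/500 + p₂(1−p₂)/6000)}.

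For 3% and RR 2: p̄ = (15 + 360)/6500 = 0.0577, the numerator is 0.0300 − 0.0213 = 0.0087, the denominator is 0.0082, and power is 0.856, as stated. The other five entries also reproduce to three decimals.

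**2. Bias when the share of 'Others' is balanced but its contents are not.** Take a true RR of 1. Let s be the share of 'Others' (equal in both weighted cohorts, so its ASD is 0), a and b the higher-risk fraction within it for comparator and target, and r the risk of that subtype relative to everyone else. Then

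spurious RR = [1 + s·b·(r−1)] / [1 + s·a·(r−1)].

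The documents give none of s, a, b or r; all are assumed. The main range is s = 10–20%, a = 10%, b = 20–30%, r = 2–3. The last row goes beyond it.

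| s | a | b | r | calculation | factor |
|---|---|---|---|---|---|
| 0.10 | 0.1 | 0.2 | 2 | 1.02/1.01 | 1.010 |
| 0.15 | 0.1 | 0.3 | 3 | 1.09/1.03 | 1.058 |
| 0.20 | 0.1 | 0.3 | 3 | 1.12/1.04 | 1.077 |
| 0.20 | 0.1 | 0.4 | 3 | 1.16/1.04 | 1.115 |

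**3. A wider grid.** Take r = 2, 3 or 5 and target versus comparator fractions of 50% vs 40%, 50% vs 30% or 60% vs 20%.

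| s | smallest factor | largest factor |
|---|---|---|
| 5% | 1.005 | 1.08 |
| 10% | 1.01 | 1.15 |
| 20% | 1.02 | 1.28 |
| 30% | 1.03 | 1.39 |

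At 5–10%, 17 of the 18 combinations stay below 1.08. Factors above 1.2 need 'Others' at 20–30%, a 3- to 5-fold subtype risk and the 60% vs 20% split together. Swapping the mix between devices inverts each factor; an equal mix gives 1.00.

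**4. What such factors would do**, in the unweighted Table 2 setting:

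- A factor of 1.05 raises the one-sided 0.025 error to 0.032 (2% risk) or 0.035 (3%); a factor of 1.10 raises it to 0.042 or 0.048.
- A factor of 0.95 at true RR 2 lowers power from 0.856 to 0.776 (3%) or from 0.642 to 0.551 (2%).
- For comparison, sampling error alone at RR 1 and 3% risk gives SE(log RR) = √(0.97/15 + 0.97/180) = 0.265, so a 95% interval from 1/1.68 to 1.68. At 2% it runs from 1/1.89 to 1.89.

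**5. Room for splitting the level.** The feasibility count for the comparator is "Among those, 526 underwent a left-sided colorectal surgery". If 'Others' is 10% of them, it holds 526 × 0.10 ≈ 53 patients and, at 2–3% risk, 1 to 2 events.

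**The case against.** A reader might infer that the score cannot balance this case mix at all. The documents do not support that. It also holds surgical site, approach, admission type, age, CCI, malnutrition, immunosuppression (with long-term systemic steroids) and prior or same-day diverting stoma. These are partial proxies for what sits in 'Others', and the formula above gives them no credit. Exclusion criterion 3 also removes patients with a Table A-2 code flagged present on admission, which weakens the inflammatory bowel disease mechanism. It does not remove patients who have the disease but no such flagged code.

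A reader might also infer that the indications in 'Others' have very different leak-code risks and are unevenly spread across devices. The documents give no risk by indication and no make-up by device. Section 6.8 shows that overall use differs: left-sided surgery is 526/623 = 84% of Tri-Staple patients, against about 6,000 of more than 10,000 (at most about 60%) for Ethicon and about 6,000/13,000 = 46% for DST. That makes an equal mix unsafe to assume, but says nothing direct about left-sided patients in 'Others'. Nor do the documents say that stoma closures enter the cohort; that depends on Table A-1's excision and repair codes.

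Finally, any category can hide heterogeneity: Table A-5 also pools diverticulitis (K57.2) with diverticular disease (K57.3). How finely to split is partly the analyst's choice, and about 526 comparators do not allow many levels. This limits the remedy. It does not excuse a malignant level that leaves out malignancies.

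**Conclusion.** The coding gap is certain: six codes define the malignant level, and every other cancer joins inflammatory bowel disease and other non-cancer diagnoses in one residual level. It is also certain that the ASD check and regression fallback, applied to this variable, cannot show or mend an uneven mix inside it. The affected Table B-6 strata are mis-specified whatever the bias.

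The effect on the two primary relative risks is of unknown direction and probably modest: about 1.01 to 1.08 under the main assumptions, nil if the mix is equal, and beyond 1.2 only under an extreme combination. These figures rest on assumed inputs and on no help from the other covariates. The main range is small beside the sampling error, but a larger sample would not remove it. The change is worth making because the main part costs almost nothing.

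**What to change.** - In Table A-5 and section 6.6.2, let 'Malignant neoplasms' take any malignant principal diagnosis. This adds no propensity term and corrects both the covariate and the Table B-6 stratum.
- In the outcome-blinded balancing step of section 6.9.2, tabulate the size and leading codes of 'Others' by device.
- Add an 'Inflammatory bowel disease' level where comparator counts allow, and merge it back into 'Others' if it is nearly empty.
- Add a stoma-closure level only if the tabulation shows that such admissions enter through the Table A-1 codes.
- Use the revised levels in the score, in Tables B-2 to B-6 and in Tables C-1 to C-8.

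The cost is a few extra codes from a field already read, and at most one or two more propensity terms with about 526 comparators. Sparse levels could produce extreme weights, so the merging decision should rest on counts alone, before outcome data are opened.
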